**LIST OF ABBREVIATIONS**

ACOG	The American Congress of Obstetricians and Gynecologists
AE	Adverse Event
CHP	Certified Healthcare Provider
CI	Confidence Interval
CFR	Code of Federal Regulations
CTCAE	Common Terminology Criteria for Adverse Events
FDA	Food and Drug Administration
GCP	Good Clinical Practice
hCG	Human Chorionic Gonadotropin
HIPAA	Health Insurance Portability and Accountability Act of 1996
IRB	Institutional Review Board
LLC	Limited Liability company
Mcg	Micrograms
Mg	Milligrams
OCP	Ontario College of Pharmacists
PI	Principal Investigator
REMS	Risk Evaluation and Mitigation Strategy
SAE	Serious Adverse Event
SAP	Statistical Analysis Plan
UC	University of California
UCSD	University of California San Diego
UCSF	University of California San Francisco
US	United States

**PROTOCOL SYNOPSIS**

TITLE	Alternative Provision of Medication Abortion via Pharmacy Dispensing
SPONSOR/PI	[name]
FUNDING ORGANIZATION	Fidelity Charitable
NUMBER OF SITES	6

**RATIONALE**

The proposed study aims to investigate the feasibility, acceptability, and effectiveness of pharmacy dispensing of Mifeprex®; safety data will also be collected. The results of this study eventually could lead to changes in the Mifeprex® REMS that would improve access to legal, safe abortion services in the US.

Trained pharmacists already successfully deliver care related for stigmatized health conditions, including sexually transmitted infections, family planning, and emergency contraception. In addition, pharmacy dispensing of mifepristone is already a reality in other countries, such as Australia, where it has improved access to medication abortion, particularly in rural areas (Grossman, 2015); pharmacy dispensing is also being implemented in Canada (OCP, 2017).

Pharmacy dispensing of Mifeprex® by trained pharmacists could improve access to medication abortion for women. Pharmacy dispensing could allow women to bypass geographical, financial, or insurance obstacles to clinic-based care and receive abortion care earlier in pregnancy (Drey et al., 2006; D. A. Grossman, Grindlay, Buchacker, Potter, & Schmetzmann, 2013; Jerman, Frohwirth, Kavanaugh, & Blades, 2017) and help to facilitate provision of medication abortion through telemedicine, reducing the disparity in access between rural and urban settings (D. Grossman, Grindlay, Buchacker, Lane, & Blanchard, 2011; D. A. Grossman et al., 2013). In light of a declining number of abortion providers in the US (Jones & Kooistra, 2011, Jones & Jerman, 2014), pharmacy dispensing could also help increase the number of clinicians willing and able to provide medication abortion by enabling them to avoid the associated costs and logistical challenges of stocking and dispensing the medication at their facilities.

Pharmacy dispensing of mifepristone would not affect the standard of care or recommended clinical protocol for medication. Mifeprex® would still be prescribed to patients by clinicians who are certified prescribers of Mifeprex® following the current standard assessment of eligibility for medication abortion. The only difference in this study is that the patient would obtain the mifepristone directly from the pharmacist, rather than in a clinic facility. In most settings women go to a pharmacy for pain medications and anti-emetics, and sometimes for misoprostol.

Home administration of Mifeprex® is now allowed under the updated Mifeprex® labeling (FDA, 2016a). Study participants will be told by the prescribing clinician when they should take the Mifeprex®, and participants will be contacted the following day to determine if they took the medication as prescribed.

STUDY DESIGN	This is a phase 4 prospective cohort study.
PRIMARY OBJECTIVE	Our primary objective is to assess the feasibility of pharmacist dispensing of Mifeprex® by measuring pharmacist satisfaction and the proportion of pharmacists who refuse to dispense the medication to patients.
SECONDARY OBJECTIVES	Secondary objectives include assessing patient satisfaction with the pharmacy-dispensing model; describing clinical outcomes, including effectiveness and adverse events, with pharmacist-dispensed Mifeprex®; and comparing pharmacist knowledge about medication abortion before and after the intervention.
NUMBER OF SUBJECTS	300 patients and 50 pharmacists
SUBJECT SELECTION CRITERIA	
Inclusion Criteria: All pharmacists providing services at one of the study pharmacies during the study; and English- or Spanish-speaking women age 15 or older (18 or older at Kaiser Permanente) seeking medication abortion through 70 days' gestation and eligible for Mifeprex® at a study clinical site. Participants must be willing and able to participate in the study, including being willing to go to the study pharmacy to obtain mifepristone and willing to take misoprostol dosage via the buccal route of administration.
 
Exclusion Criteria: We will exclude women who are not pregnant or not seeking medication abortion, under the age of 15, (or under the age of 18 at Kaiser Permanente) who have contraindications for medication abortion, or who choose to administer misoprostol vaginally instead of buccally.

TEST PRODUCT, DOSE, AND ROUTE OF ADMINISTRATION	Oral Mifeprex® 200 mg followed by misoprostol 800 mcg administered buccally (at 24-48 hours following mifepristone).
DURATION OF SUBJECT PARTICIPATION AND DURATION OF STUDY	
The duration of the study will be 24 months. Most patient subjects' participation will end after completing the Day 14 Survey approximately 2 weeks after taking Mifeprex®. Adverse events (AEs) will be captured up to 6 weeks after Mifeprex®, and any ongoing will be followed until resolution.
 
Pharmacists' participation in the study will continue throughout the study, although data will be collected from them only at specific time points before launching the study and at the end of the study.

CONCOMITANT MEDICATIONS	Allowed: Any Prohibited: None
EFFICACY EVALUATIONS	The UCSF study team will train sites on standardized recruitment and consent procedures and have regular communication with study clinics and

	pharmacies to provide technical assistance and check on progress of study. Data collection tools and procedures will be pilot tested before implementation. Data will also be monitored periodically to ensure that data collection, coding, and management procedures are being conducted according to protocol and ethical guidelines.
PRIMARY ENDPOINT	The primary outcome will be feasibility of dispensing of Mifeprex® by pharmacists, measured by pharmacist satisfaction and the proportion of pharmacists refusing to dispense.
SECONDARY ENDPOINTS	Secondary outcomes will include patient satisfaction and clinical outcomes of patients who receive Mifeprex® dispensed in the pharmacy.
OTHER EVALUATIONS	N/A
SAFETY EVALUATIONS	Data abstraction of electronic health records will provide clinical data for analysis. We will conduct quantitative analyses of clinical data and the PI will track all reports of adverse events and serious adverse events to monitor safety.
PLANNED INTERIM ANALYSES	No formal interim analysis is planned. Serious and unexpected adverse events will be monitored on an ongoing basis throughout the study.
STATISTICS Primary Analysis Plan	We will use descriptive analyses using chi-square and t tests where appropriate to assess pharmacist satisfaction and patient satisfaction with the model and clinical outcomes of patient participants.
Rationale for Number of Subjects	
We aim to recruit up to 350 patients for this pilot study, which is a feasible sample at the study sites. With a sample size of 350, if the proportion of patients with a complete abortion is 95%, the 95% confidence interval of that proportion will be +2.7%. Abortion completion is an important clinical outcome.
 
We aim to survey all the pharmacists at the study sites, up to 50. This sample size will be determined by the number of pharmacists at the study sites.

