### 13.3 Replacement of Subjects

If any subject withdraws or does not complete the study as planned, they will be replaced with an additional participant.

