## 16.6 Sample Size

We aim to recruit 350 patients for this pilot study, which is a feasible sample at the study sites. With a sample size of 350, if the proportion of patients with a complete abortion is 95%, the 95% confidence interval of that proportion will be  $\pm 2.7\%$ . Abortion completion is an important clinical outcome.

We aim to survey all the pharmacists at the study sites, up to 50. This sample size will be determined by the number of pharmacists at the study sites. We have confirmed that there is at least one pharmacy at the site who is willing to dispense mifepristone, which is sufficient for the study. In the unlikely event that a willing and trained pharmacist is not on site to dispense the medication, the patient will be told when she can return to the pharmacy to have the prescription filled. Alternatively, the patient may return to the clinic, where the mifepristone will be dispensed. If that happens, the study will still cover the cost of the medication abortion, but the patient will be discontinued from the study.

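### The stated precision of ±2.7% does not follow from n = 350 (it is ±2.3%; 2.7% is the n = 250 value), and the 300 patients given elsewhere in the synopsis do not yield it either

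*Protocol*

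**What the plan says.** Three current statements in the Protocol bear on the number of patients and the precision it buys.

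- **Synopsis, Number of Subjects row:** "300 patients and 50 pharmacists".
- **Synopsis, Rationale for Number of Subjects row:** "We aim to recruit up to 350 patients for this pilot study". It then says that, "if the proportion of patients with a complete abortion is 95" percent, "the 95% confidence interval of that proportion will be +2.7" percent. The lone plus sign is most likely a lost plus/minus sign and is not treated here as an error.
- **Section 16.6:** "We aim to recruit 350 patients for this pilot study", without the qualifier that makes 350 a ceiling. "With a sample size of 350, if the proportion of patients with a complete abortion is 95" percent, then "the 95% confidence interval of that proportion will be" ±2.7%.

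No interval method is named. No dropout allowance or clustering adjustment is stated. Section 13.3 says of patients who withdraw or do not complete that "they will be replaced with an additional participant". The SAP gives no sample size and no precision statement.

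**The concern.** The precision sentence supplies everything needed to check it: the number of patients, the assumed proportion and the confidence level. A plus/minus figure for a proportion is therefore fixed by those inputs, and the printed one does not match. The synopsis also carries two patient numbers, so it is unclear which one the precision claim is meant to describe.

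This sentence is the only quantitative support for the sample size in either document; the number of pharmacists is set by staffing at the sites. A reader who repeats the calculation will find that it fails. A team that has to decide when enrolment is complete, with non-completers replaced, has targets that differ by 50 patients.

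**Working it through.** **Inputs.** n = 350 (Synopsis rationale and section 16.6); n = 300 (Synopsis, Number of Subjects); p = 0.95 and a 95% level (Synopsis rationale and section 16.6); stated half-width 2.7 points.

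**Attempt to reproduce the plan's figure.** The symmetric (Wald) half-width is 1.96 × √(p(1 − p)/n), with p(1 − p) = 0.95 × 0.05 = 0.0475.

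| n | √(0.0475/n) | × 1.96 | Half-width |
|---|---|---|---|
| 350 | 0.01165 | 0.0228 | ±2.28 points |
| 300 | 0.01258 | 0.0247 | ±2.47 points |
| 250 | 0.01378 | 0.0270 | ±2.70 points |

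Solving for the n that gives 2.7 points: 1.96² × 0.0475 / 0.027² ≈ 250. Any n from 242 to 259 rounds to 2.7. The figure is not reproduced at 350 or at 300. Relative to n = 350 the stated value is too large by 2.7/2.283 − 1 ≈ 18%.

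**Other methods at n = 350.** Because 0.95 × 350 = 332.5 is not a whole number, these half-widths (half of the total width) were computed at 332.5:

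- Wald with z = 2: 2.33
- Wald with continuity correction: 2.43
- Wilson: 2.32
- Agresti-Coull: 2.37
- Jeffreys: 2.29
- Clopper-Pearson (exact): 2.44
- Wilson with continuity correction: 2.46

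Changing the confidence level does not help: Wald gives 1.92 at 90% and 3.00 at 99%. No half-width at n = 350 reaches 2.7.

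**Exact intervals at whole-number counts.**

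- 333/350 (95.14%): 92.34% to 97.15%, arms 2.81 below and 2.00 above.
- 332/350 (94.86%): 91.99% to 96.92%, arms 2.86 and 2.07.
- 285/300 (95.00%): 91.89% to 97.17%, arms 3.11 and 2.17.

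**Could an unstated allowance explain 2.7 at 350?** It would take one of the following, and the documents give none of them:

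- a loss of 1 − 250.3/350, about 28%, of the patients;
- a design effect of (2.7/2.283)², about 1.40;
- an assumed completion proportion of roughly 92.6% to 93.1% instead of 95%.

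Section 13.3 points away from the first, since it replaces non-completers. Section 16.1 restricts the patient analysis to those who receive the dose, but gives no smaller n for the precision statement.

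**The case against.** The strongest reply concerns consequence. Both places present 350 as what the sites can feasibly recruit for a pilot; the precision sentence describes what that number buys and did not determine it. The error is conservative: the true half-width is about 0.4 points narrower at 350 (2.70 − 2.28 = 0.42), and even at 300 the Wald value is below 2.7. The outcome is secondary and descriptive, the primary endpoint concerns pharmacists, and nothing in the SAP depends on the figure. All of this stands. It limits the weight of the point, but a stated precision that its own inputs contradict still needs correcting.

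A second reply is that no interval method is named, and some come close. At n = 350 the lower arm of the Jeffreys interval is 2.66 points. However, its upper arm is 1.92, so this is not a plus/minus figure. At n = 300, half the width of the continuity-corrected Wilson interval is 2.68, which rounds to 2.7. That interval is also asymmetric (3.29 below, 2.07 above), it is an uncommon choice for such a statement, and the Protocol ties 2.7 to 350. So the statement that 300 does not give 2.7% holds for the usual symmetric formula, not for every conceivable method.

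A third reply is that a ceiling of 350 is not strictly incompatible with 300. That is fair for the two synopsis rows taken alone. Section 16.6 gives 350 as the aim, however, so the Number of Subjects row still has to be reconciled with it.

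Finally, neither document mentions n = 250. That 2.7% survived from a plan of that size is consistent with the arithmetic but is only an inference, and the conclusion does not need it.

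**Conclusion.** The concern holds. At n = 350 and 95% completion the 95% half-width is ±2.3 points, not ±2.7; at n = 300 it is ±2.5; ±2.7 corresponds to about 250 patients. Separately, the synopsis gives 300 patients in one row and up to 350 in another, while section 16.6 aims for 350.

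This rests on reading the plus/minus statement as a symmetric interval for independent patients with the full stated n analysed, which is how the Protocol presents it. The effect is modest: the sentence understates the precision at 350, biases no analysis, and by itself calls for no change in enrolment. It should be corrected because the stated sample size and precision do not agree.

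**What to change.** Choose one patient number and use it in the Synopsis (Number of Subjects and Rationale for Number of Subjects) and in section 16.6. Restate the precision to match, and name the method.

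- **If 350:** ±2.3% (Wald) or, preferably for a proportion near 95%, the exact interval, for example 92.34% to 97.15% with 333 of 350 complete.
- **If 300:** ±2.5% (Wald), or exact 91.89% to 97.17% with 285 of 300 complete.

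If the authors intended an allowance for loss or clustering, or a different assumed proportion, they should state it and show the n used. Restore the plus/minus sign in the synopsis at the same time.

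The cost is wording only, and enrolment does not change if 350 is confirmed. Sections 18.1 and 18.2 require prior IRB approval for amendments, apart from urgent safety changes and, in 18.2, purely logistical or administrative ones. The team would need to settle whether restating the patient number falls under that last exception.

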## 1 BACKGROUND

Medical termination of intrauterine pregnancy, also known as medication abortion, is a safe and effective alternative to surgical abortion (vacuum aspiration). Mifeprex® (generic: mifepristone), which is a progestin antagonist that competitively interacts with progesterone at progesterone- receptor sites, used together with misoprostol is the gold standard regimen for medication abortion. In studies performed in the United States up to 70 days gestation using this dosing regimen, 97.4% of patients reportedly had a complete abortion (FDA, 2016a). Another 2.6% received surgical intervention, or vacuum aspiration, for reasons such as ongoing pregnancy, patient request, bleeding, medical necessity and incomplete expulsion.

Medication abortion up to 70 days gestation with mifepristone 200 mg orally followed by misoprostol 800 mcg administered via the buccal or vaginal route has a favorable safety profile. Although serious and sometimes fatal infections have been reported with this treatment, this complication is very rare; only 8 deaths related to sepsis have been reported among almost 3 million uses of the medication (FDA, 2011). Uterine bleeding requiring medical or surgical intervention is also a known complication of the treatment. Heavy bleeding requiring surgical treatment occurs in approximately 1% of patients, and blood transfusion is required in <0.1%. Adverse events that are more common include nausea, vomiting, weakness, fever/chills, headache, diarrhea and dizziness (FDA, 2016a).

In March 2016, the Food and Drug Administration (FDA) approved an updated label for Mifeprex® to reflect recent research published since the drug's original approval in 2000 (FDA, 2016a). The approved dosing regimen includes oral mifepristone (200 mg) followed by a dose of misoprostol (800 mcg) administered buccally 24-48 hours later. The changes made to the label included a more effective dosing regimen containing less mifepristone (200 mg instead of 600 mg) and more misoprostol (800 mcg instead of 400 mcg) via the buccal route, extension of the gestational age limit for treatment from 49 to 70 days, removal of the recommendation for in-person follow-up, removal of language indicating that the prescriber must be a physician, and elimination of the requirement to report nonfatal adverse events to Danco Laboratories, LLC, the drug's US distributor, and the FDA.

In addition, the updated label no longer requires that Mifeprex® or misoprostol be taken in the facility where they are dispensed. A systematic review of nine studies with over 4,500 participants compared outcomes of those who took misoprostol at home to those who took it in a clinical setting (Ngo, Park, Shakur, & Free, 2011). Complete abortion and complication rates were not different between the groups, but women who used misoprostol at home were more likely to be satisfied and recommend the method to a friend. In one US study of 400 women at six sites, 32% chose to take mifepristone at home, and complete abortion rates were similar between those who took the drug in the clinic and at home (96%-97%) (Chong et al., 2015). Among those who took mifepristone at home, 82% reported taking the medication at the time they planned with their provider, and no participant took it after 63 days gestation which was the gestational age limit at the time of the study.

In addition to buccal administration, misoprostol 800 mcg is commonly administered vaginally in an off-label regimen for medication abortion, which is also recommended by the American College of Obstetricians and Gynecologists (ACOG, 2014). This regimen allows for a shorter interval between the two medications, which some patients prefer. Up to 63 days gestation, vaginal misoprostol given at the same time as mifepristone results in complete abortion in approximately

95% of cases (Creinin et al., 2007). Another common regimen involves administering misoprostol 800 mcg vaginally 6-8 hours after mifepristone, which has a complete abortion rate of 95.8% up to 63 days gestation and fewer side effects compared to a 24-hour dosing interval (Creinin et al., 2004).

Numerous studies performed in the US and other countries have demonstrated that medication abortion has a high level of acceptability for a majority of women seeking pregnancy termination (Beckman & Harvey, 1997; Christin-Maitre, Bouchard, & Spitz, 2000). In a meta-analysis of approximately 4,500 patients who underwent pregnancy termination with mifepristone and misoprostol, over 85% of women were satisfied with the experience (Ngo et al., 2011). Medication abortion accounts for a growing share of US abortions, from 17% of non-hospital procedures in 2008 to 31% in 2014 (Jones, 2017). Medication abortions accounted for 45% of all abortions up to nine weeks gestation in 2014, up from 26% in 2008 (Jones, 2017).

Some evidence suggests that improved access to mifepristone is associated with a reduction in the proportion of abortions performed in the second trimester, which is important from a public health perspective because later abortion is associated with a significantly increased risk of complications and death compared to early abortion (Zane et al., 2015). In one study in Iowa, development of a program providing medication abortion using telemedicine was associated with a significant increase in the proportions of abortion that were performed with medication. After controlling for other factors, women seeking abortion in the two years after telemedicine was introduced had a significantly higher odds of obtaining a first-trimester abortion compared to the two years prior (D. A. Grossman et al., 2013). Conversely, in Texas, second-trimester abortion increased by 27% in the year after restrictions on access to abortion were imposed, including limitations on the use of medication abortion that led to a 70% decline in use of this method (D. Grossman, 2017).

Despite the increasing use of medication abortion, there is evidence that some women face barriers accessing this method, and this can be particularly distressing when they have a strong preference for the method (Baum, White, Hopkins, Potter, & Grossman, 2016). In particular, the closure of abortion facilities across the country (Deprez, 2016), which has increased the distance women must travel to access abortion care, may make it harder to access medication abortion. The longer travel distances, which increase the cost and logistical difficulty of getting to a clinic, may create delays that push women past the gestational age limit for medication abortion (Baum et al., 2016; Fuentes et al., 2016).

Medication abortion in the US is primarily offered by existing abortion providers. Uptake of medication abortion provision among private physicians has been less than expected—especially in areas not served by providers of surgical abortion. In 2005, there were only four providers of Mifeprex® medication abortion that were located more than 50 miles from any surgical abortion provider (Finer & Wei, 2009). One reason for the lack of uptake among private physicians may relate to the Mifeprex® Risk Evaluation and Mitigation Strategy (REMS) program.

The Mifeprex® REMS program has three components (FDA, 2016b):

1. Prescribers must be certified with the program by completing the Prescriber Agreement Form
2. Patients must sign a Patient Agreement Form.
3. Mifeprex® must be dispensed to patients only in certain healthcare settings, specifically clinics, medical offices and hospitals, by or under the supervision of a certified prescriber.

This third component requires that prescribers stock the medication in their facilities in order to dispense it on site. A qualified clinician who has not completed the certification process and arranged to stock the drug in his or her office cannot provide timely medication abortion care to a woman who presents unexpectedly. Consequently, treatment of such a patient would be delayed, which might increase her medical risks (Bartlett et al., 2004; Mifeprex REMS Study Group, 2017).

We recently explored this issue in a survey of practicing obstetricians-gynecologists (Grossman et al., 2017). In 2016-2017, we performed a survey with a representative sample of Fellows of the American College of Obstetricians and Gynecologists. The survey was sent by email with an online link, and non-responders were mailed paper surveys. 1,284 currently practicing Fellows responded to the survey (response rate 54%). 99% reported seeing patients of reproductive age; among these, 1,155 were included in this analysis. 75% reported having a patient in the prior year who needed or wanted an abortion. Only 23% (95% CI 21%-25%) reported performing an abortion in the prior year; 10% provided surgical and medication abortion, 9% surgical only, and 4% medication only.

Among those not providing medication abortion, 19% said they would provide the method if they could write a prescription for mifepristone and their patients could obtain the medication at a pharmacy. An additional 18% said they were unsure if they would provide medication abortion in this scenario. Our findings suggest that the proportion of obstetrician-gynecologists providing medication would at least double (from 14% to 29%) if the dispensing restriction in the REMS were removed and physicians could write a prescription for Mifeprex® that could be dispensed at a pharmacy.

Given this evidence that the dispensing requirement represents a barrier to access, we propose to perform a study of the feasibility of pharmacy dispensing of Mifeprex®. For this study, all clinical activities will remain consistent with the current standard of care and Mifeprex® REMS program except for the dispensing of Mifeprex®. In particular, patients will be evaluated for all contraindications to the method according to the label, and they will sign the Patient Agreement Form. A clinician who has completed the Prescriber Agreement Form will write a prescription for Mifeprex® 200 mg for the eligible patient. The patient will then go to a designated pharmacy to fill the prescription, where it will be dispensed by a trained pharmacist. The patient will then take the Mifeprex® at the time indicated by the prescribing clinician. Patients will be contacted on Day 2 and Day 14 to complete surveys about their experience, and they will undergo standard clinical follow-up. In addition, we will perform surveys and interviews with pharmacists before and after initiating the study, as well as monitor the number of pharmacists who refuse to dispense Mifeprex® at the study pharmacies.

